6.5.4. SARS-CoV-2 functional cross-neutralization of variant B.1.351 to reference strain

Definition

The SARS-CoV-2 functional cross-neutralization of variant B.1.351 to reference strain is defined as the ratio of the GMT (reference / variant B.1.351). The geometric mean titer ratio is calculated as the GMT of reference divided by the GMT of variant B.1.351.

Analysis

For subjects of Group A, GMTs with 95% CI for all time points will be presented for variant B.1.351 and reference strain (see Section 6.5.1). Moreover, the GMT ratio between reference and variant will be presented.

6.6. Sensitivity analyses

Sensitivity analyses of immunogenicity endpoints (see Section 6.5) may be conducted as appropriate by excluding subjects with a SARS-CoV-2 infection during the BNT162-14 trial.

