8.2.8 Serum for nucleocapsid protein testing

Blood will be drawn by trial site personnel for nucleocapsid ELISA SARS-CoV-2 testing at the time points provided in the SoA (Section 1.3); this will use blood draw for Neutralizing antibody titers and antibody binding (NATAB) (see Section 8.10.1).

Nucleocapsid ELISA SARS-CoV-2 testing will be performed at a central laboratory.

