5.1. Definition of analysis sets

Screened set (SCR)

The screened set is defined as all subjects who signed informed consent.

Safety set (SAF)

The safety set is defined as all subjects who received at least one dose of investigational medicinal product (IMP).

Safety boost set (SAFB)

The safety boost set is defined as all subjects who received two doses of IMP (first injection (Dose 1) and second injection (Dose 2)).

Note: Group A will be excluded from the SAFB as they receive only a single injection according to protocol.

Immunogenicity set (IMM)

The immunogenicity set is defined as all subjects who received at least one dose of IMP and have at least one post-baseline functional antibody titer (e.g., VNT or an equivalent assay) immunogenicity assessment.

Note: The expression 'have at least one post-baseline functional antibody titer immunogenicity assessment' refers to having either at least one post-baseline neutralizing antibody titer or one post-baseline ELISA titer immunogenicity assessment.

Immunogenicity per-protocol set (IMMPP)

The immunogenicity per-protocol set is defined as all subjects included in the immunogenicity set that have no major protocol deviations as determined by the clinician and who received two doses of IMP (first injection (Dose 1) (for Group A and B) and second injection (Dose 2) (only for Group B)).

Note: Subjects with any major protocol deviation thought to interfere with either the mechanism of action or immunogenicity test measurements will be excluded from IMMPP set.

Note: The definitions of all analysis sets apply within the BNT162-14 trial. In all analysis sets, subjects will be assigned to the treatment groups (i.e., vaccine type) according to the actual treatment they received ("as treated"). The condition of receiving two doses of IMP will not apply to Group A.

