5.2. Protocol deviations

Protocol deviations are failures to adhere to the inclusion/exclusion criteria and protocol requirements and will be classified into major and minor protocol deviations. They will include, but are not limited to, protocol deviations from the site and process deviations tracked by the sponsor.

Major protocol deviations will be identified by medical review prior to database snapshot for main analysis.

The following criteria must be considered as major protocol deviations:

- 1. Violation of major inclusion or exclusion criteria
- 2. Assignment to incorrect vaccine/dose (i.e., actual vaccine/dose taken differs from the scheduled)
- 3. Non-compliance (e.g., no vaccine was administered)
- 4. Intake of prohibited concomitant medication
- 5. Missing primary endpoint data
- 6. Delayed safety reporting
- 7. Study assessments prior to signing informed consent form
- 8. Signing a non-approved version of the informed consent form.

PDs related to COVID-19 will be reported.

Major protocol deviations will be presented in a listing including information on treatment group, site, description of protocol deviation, classification, reason for deviation, coded term, date of occurrence and subject exclusion. For each group, vaccine and subgroup, the number and percentage of subjects with major protocol deviations will be summarized in total, by site and by protocol deviation type.

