6.1. General considerations

No formal statistical testing will be done.

Unless otherwise specified, analyses will be based on data pooled across all study sites within the BNT162-14 trial.

Data assessed after a vaccination with a non-trial SARS-CoV-2 vaccine will be excluded from all statistical analyses (tables and listings) accordingly.

Notes:

- Data assessed on the same day as the non-trial vaccination will remain in the analysis.
- If the date of non-trial vaccination is missing, but month and year information is available, data assessed after the last day of the respective month will be excluded from statistical analysis.

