6.5. Secondary endpoint analyses

Secondary endpoints are neutralizing antibody titers and antibody titers (ELISA) to recombinant S1 and RBD protein derived from reference and SARS-CoV-2 variant B.1.351 (B.1.351 for Group A only) and SARS-CoV-2 functional cross-neutralization of variant B.1.351 to reference strain (for Group A only). All secondary analyses will be performed using the IMM and possibly additionally the IMMPP population, see Section 5.1.

Any COVID-19 vaccination that a subject received outside of this trial will be considered as concurrent event and all immunogenicity data assessed beyond this event will be excluded from the immunogenicity analyses.

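### Titers taken after a SARS-CoV-2 infection stay in the immunogenicity summaries, and the only provision for infection is optional, undefined and removes whole subjects

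*SAP*

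**What the plan says.** **Non-trial vaccination.** SAP 6.1 is mandatory: "Data assessed after a vaccination with a non-trial SARS-CoV-2 vaccine will be excluded from all statistical analyses". SAP 6.5 applies the same rule to titers: "Any COVID-19 vaccination that a subject received outside of this trial will be considered as concurrent event". Titers taken later are then dropped. Only data after the event are lost.

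**Infection.** Neither section mentions it. The immunogenicity set (SAP 5.1) asks for at least one dose and that subjects "have at least one post-baseline functional antibody titer" assessment; it has no infection criterion. For the per-protocol set, SAP 5.1 notes: "Subjects with any major protocol deviation thought to interfere with either the mechanism of action or immunogenicity test measurements will be excluded from IMMPP set". SAP 5.2 then introduces eight items with "The following criteria must be considered as major protocol deviations", and SARS-CoV-2 infection is not among them. SAP 6.1.1 makes the per-protocol repeat optional, although protocol 9.4.3 says it will be done. SARS-CoV-2 test results are only listed (SAP 6.8.4).

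**The one provision.** SAP 6.6 says that sensitivity analyses of the immunogenicity endpoints "may be conducted as appropriate by excluding subjects with a SARS-CoV-2 infection during the BNT162-14 trial". It does not say which test or event counts as infection, or how infection is dated.

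**Data collected.** Protocol 8.2.7 and the schedules provide surveillance NAAT swabs from Visit 2 onward. Protocol 8.2.8 takes nucleocapsid serology from the same blood draw as the titers: "Nucleocapsid ELISA SARS-CoV-2 testing will be performed at a central laboratory".

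**The concern.** Protocol 4.2 gives the durability and breadth of the vaccine-induced response as part of the scientific rationale. An infection, like a non-trial vaccine, is a further antigen exposure that is not the trial product. A titer taken afterwards mixes the two, and the SAP states no strategy under which that mixture is the intended quantity.

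Infections are expected: sequencing virus from infected subjects is an exploratory objective, and SAP 1.2 foresees breakthrough infection in transplant subjects. The visits most exposed are Weeks 12 and 26, and the later post-Dose 2 visits in the 15 transplant subjects, where protocol 2.2 makes the persistence of titers an explicit question. Infection boosts there could look like durability.

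The optional remedy has its own weakness. It conditions on an event after vaccination and removes all of the subject's titers, including those from before the infection.

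**Working it through.** The documents give no infection rate, boost size or expected titer, so there is no planned figure to reproduce. Every size below is an assumption shown over a range.

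**1. Boost in the GMT.** Let a share p of subjects be infected before a visit and let infection multiply the titer by f. The mean log titer rises by p × ln f, so

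GMT inflation = exp(p × ln f) = f^p.

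The GMFR inflates by the same factor, because the baseline precedes the infection.

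- p = 10%, f = 3: 3^0.10 = 1.12
- p = 20%, f = 5: 5^0.20 = 1.38
- p = 30%, f = 10: 10^0.30 = 2.00

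| p | f = 4 | f = 10 | f = 20 |
|---|---|---|---|
| 5% | 1.07 | 1.12 | 1.16 |
| 10% | 1.15 | 1.26 | 1.35 |
| 20% | 1.32 | 1.58 | 1.82 |
| 30% | 1.52 | 2.00 | 2.46 |

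The formula takes the full boost as present at the visit. It ignores waning after an early infection and infections too recent to have raised the titer, so it is an upper-end approximation.

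**2. Transplant subjects (n = 15).** With f = 10, one infected subject gives 10^(1/15) = 1.17 and three give 10^(3/15) = 1.58.

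**3. Group A arms.** At most 90 subjects randomized 2:1 gives 60 and 30. A 10-point difference in infection rate between arms would by itself produce a GMT ratio of f^0.10, which is 1.15, 1.26 or 1.35 for f = 4, 10 or 20.

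**4. Seroconversion.** SAP 6.5.3 uses all subjects with data at the visit as the denominator. If the true rate is s and every infected subject converts, the observed rate is s + (1 − s) × p. For s = 50% this is 52.5%, 55%, 60% and 65% at p = 5%, 10%, 20% and 30%.

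**5. Cross-neutralization.** SAP 6.5.4 uses GMT(reference) / GMT(B.1.351). If infection multiplies the two titers by f_R and f_V, the ratio changes by (f_R / f_V)^p. It is unaffected if the boosts are equal and moves in either direction if they are not.

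**6. Whole-subject exclusion against dropping titers from infection onward.** This was simulated with 2,000,000 subjects. Assumptions: ln titer at Week 4 with SD 1; Week 26 ln titer = −1.5 + 0.8 × Week 4 value + normal error with SD 0.6; infection after Week 4 by a logistic model on Week 4 ln titer; p = 10% to 30%; f = 10. Entries are the estimated GMT divided by the infection-free GMT.

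| Odds ratio of infection per ln unit of titer | Week 4, whole subjects excluded | Week 4, titers dropped from infection on | Week 26, all data | Week 26, either exclusion |
|---|---|---|---|---|
| 1.0 (titer unrelated to infection) | 1.00 | 1.00 | 1.26–1.99 | 1.00 |
| 0.7 | 1.04–1.11 | 1.00 | 1.26–1.99 | 1.03–1.09 |
| 0.5 | 1.07–1.21 | 1.00 | 1.26–1.99 | 1.05–1.17 |

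The two exclusions agree at Week 26. They differ at the visit before infection, and only if low titer predicts infection.

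**The case against.** **The late-visit answer is the same.** A reader might infer that dropping titers from infection onward corrects Week 26 better than 6.6 would. It does not: the two give the same Week 26 values, with up to about 1.17 residual selection in the simulation. Early visits in the all-data analysis carry little infection boost anyway, so all-data and 6.6 together could cover most needs. This stands. What it leaves is that 6.6 need not be run, has no definition of infection, and discards usable titers.

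**Selection is not established.** A reader might infer that whole-subject exclusion necessarily favors better responders. Protocol 2.2 says no titer level linked to lower infection risk, and no functional correlate of protection, had been determined, although it also applies a titer-based predictive model. With no link the Week 4 bias is nil. This stands, so the bias is only possible.

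**The two events differ.** Vaccination has a recorded date, and the schedules stop sampling after it. Sampling continues after infection, which may be detected only at a visit up to 14 weeks after the last one (Week 12 to Week 26). Different handling is therefore not an inconsistency in itself. True, but nucleocapsid testing on the titer sample is enough to classify that sample.

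**A simple first-positive rule would misfire.** Entry bars only infection diagnosed in the 12 weeks before Day 1, so a subject may already be nucleocapsid-positive at baseline. Censoring at any first positive sample would remove all of that subject's titers. This stands and shapes the fix.

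**The stakes are descriptive.** No hypothesis is tested, and both titers and SARS-CoV-2 results are listed by subject. Keeping all data would be defensible as a stated treatment-policy summary. The SAP states none, and listings do not give a reader a GMT free of infection boosts.

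**Conclusion.** The concern holds in a limited form. Post-infection titers remain in all the SAP 6.5 summaries, and neither analysis set removes them by rule. The per-protocol set may lose an occasional infected subject, such as a transplant subject who misses Dose 2, but only incidentally and as a whole subject.

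The effect is on the reading of late-visit estimates, not on type I error or power. Inflation of 1.12 to 2.0 rests entirely on assumed infection shares (10% to 30%) and boosts (3- to 10-fold). A reader might take the twofold figure as an expected error; the documents do not support that, since it pairs the highest assumed rate with the highest assumed boost and takes the boost as fully present.

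Upward bias in early-visit GMTs under 6.6 (1.00 to 1.21 at Week 4 in the simulation) is possible only if low titer predicts infection. The gain from a change is an analysis that is guaranteed, has a dated definition of infection, and keeps pre-infection titers.

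**What to change.** Keep the all-data analysis and replace SAP 6.6 with a mandatory analysis:

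- Use each subject's titers up to the first evidence of infection after Day 1. That is the first positive NAAT (surveillance or ad hoc), or the first nucleocapsid-positive sample in a subject who was nucleocapsid-negative at BNT162-14 baseline, whichever comes first.
- Exclude titers from that date or sample onward, including the newly positive sample itself, because the infection preceded it. This differs from SAP 6.1, which keeps same-day data for a non-trial vaccination.
- Keep subjects who are nucleocapsid-positive at baseline, flag them, and censor them only on a new positive NAAT.
- Report the number censored by visit and arm, and state that some late-visit selection may remain.

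The cost is SAP wording, one extra set of titer tables and fewer late titers in that set. No new sampling is needed.

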6.7. Exploratory analyses

Exploratory analyses are out of scope of this SAP and may be described in a different document.

6.8. Further safety analyses

All analyses will be performed in the SAF for Group A and the immunology subset of Group B.

Safety data that will be presented includes IMP compliance, clinical laboratory assessments and vital signs.

6.8.1. Compliance

IMP compliance will be summarized.

Time of first injection after receiving the last BNT162 candidate vaccine in the BNT162-01 or BNT162-04 trial and Time of second injection after receiving the first injection will be summarized.

Drug exposure will be listed.

6.8.2. Laboratory assessments

Definition

Clinical laboratory data to be summarized includes hematology, clinical chemistry, and urinalysis and will be assessed at the time-points indicated in Tables 1, 2, 2a, and 3 of the protocol.

The following clinical laboratory variables will be assessed:

Hematology

Hemoglobin, hematocrit, red blood cell count, white blood cell count and differential (neutrophils, lymphocytes, monocytes, eosinophils, basophils), platelet count.

Clinical chemistry

Alkaline phosphatase, creatinine, ferritin, C-reactive protein, albumin, alanine aminotransferase, amylase, aspartate aminotransferase, gamma glutamyl transpeptidase, total bilirubin, blood urea nitrogen, glucose, lipase, sodium, potassium, calcium.

Follicle-stimulating hormone: In women only.

Urinalysis

Dipstick: glucose, bilirubin, ketone, specific gravity (1 mL \triangleq 1 g), blood, pH, protein, urobilinogen, nitrite, and leukocytes.

Microscopic urinalysis: If warranted by dipstick results, urine sediment will be microscopically examined for presence of red blood cells, white blood cells, casts, crystals, epithelial cells, and bacteria.

All laboratory tests are classified as normal or lower or higher than reference range (abnormal). All abnormal laboratory tests will be classified by the investigator as clinically significant (CS) or not clinically significant (NCS).

Abnormal lymphocytes data will be categorized as defined in table 7 in the protocol as Grade 1 (mild), Grade 2 (moderate), Grade 3 (severe), and Grade 4 (potentially life-threatening).

Analysis

Clinical laboratory variables at each time-point and its change from baseline to each post-baseline time-point (for continuous variables and if applicable) will be summarized using descriptive summary statistics for each parameter.

Number and percentage of subjects with low, normal and high clinical laboratory values at each time-point will be summarized for each parameter. The same table will be provided for the grading scheme (grades mild, moderate, severe and life threatening) for lymphocytes.

The number and percentage of subjects with CS abnormal, abnormal (NCS), normal and missing values will be summarized for each parameter.

Clinical laboratory values for each parameter will be summarized using shift tables from baseline to worst post-baseline value with respect to reference range values (low, normal, high), if applicable. Worst post-baseline might be in both directions. Each subject may be counted in the parameter high and in the parameter low category. A subject will only be counted in the normal category if all post-baseline values are normal. If several post-baseline values are considered as worst post-baseline value, the first one is taken.

All clinical laboratory data will be presented in the data listings along with normal ranges abnormal clinical laboratory values will be flagged in the listing.

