9.4.5 Other safety analyses

Safety data other than AEs that will be summarized includes clinical laboratory parameters and vital signs for Group A and the Immunology Subgroup of Group B only. All safety analyses will be based on the Safety Set and will be summarized descriptively by group unless otherwise stated.

Clinical laboratory parameters for Group A and the Immunology Subgroup of Group B

The clinical laboratory parameters to be summarized and assessed for Group A and the Immunology Subgroup of Group B are listed in Section 10.2. The scheduled time points for assessment are given in the SoA (see Section 1.3).

Clinical laboratory parameters at each time point and change from baseline to each postbaseline time point will be summarized using descriptive summary statistics for each parameter by group.

Shift tables from baseline to worst intensity grade will be provided for each laboratory parameter by group.

Additionally, the occurrence of clinically significant abnormal laboratory results within a trial subject will be analyzed using descriptive summary statistics for each parameter and visit by group.

Abnormal laboratory results will be graded using criteria based on the guidance given in FDA Guidance for Industry "Toxicity Grading Scale for Healthy Adult and Adolescent Volunteers Enrolled in Preventive Vaccine Clinical Trials" (see Section 10.3.2).

Laboratory parameter results will be listed along with the normal ranges. Values that are below or above the normal ranges will be flagged.

Clinical laboratory analysis details will be described in the SAP.

Vital signs for Group A and the Immunology Subgroup of Group B

The vital sign parameters to be summarized and assessed are given in Section 8.2.2. The scheduled time points for assessment are given in the SoA (see Section 1.3).

Vital sign parameters at each time point and change from baseline to each post-baseline time point will be summarized using descriptive summary statistics for each parameter by group.

BioNTech SE	Clinical Trial Protocol
Confidential	BNT162-14

Page 60 of 91 Version: 4.0 Date: 20 JAN 2022

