If a fever of \geq 39.0°C is recorded by a subject during the 7 d post-injection diary period, a telephone contact should occur to ascertain further details and determine whether a site visit is clinically indicated. Only an investigator or medically qualified person is able to confirm a participant's fever as >40.0°C for recording the trial database. If a participant experiences a confirmed fever >40.0°C, the investigator must immediately notify the sponsor and, if it is determined to be related to the administration of IMP, further IMP injections will be discontinued in that participant.

BioNTech SE	Clinical Trial Protocol	P
Confidential	BNT162-14	Dat

Laboratory abnormalities

Laboratory abnormalities will be graded according to the grading scheme given in Table 7.

	Mild (Grade 1)	Moderate (Grade 2)	Severe (Grade 3)	Potentially life- threatening (Grade 4)
Hematology				
Hemoglobin (female) - g/dL	11.0 - 12.0	9.5 – 10.9	8.0 - 9.4	<8.0
Hemoglobin (female) change from baseline value - g/dL	Any decrease – 1.5	1.6 – 2.0	2.1 – 5.0	>5.0
Hemoglobin (male) - g/dL	12.5 – 13.5	10.5 – 12.4	8.5 – 10.4	<8.5
Hemoglobin (male) change from baseline value - g/dL	Any decrease – 1.5	1.6 – 2.0	2.1 – 5.0	>5.0
WBC increase - cells/mm ³	10,800 - 15,000	15,001 - 20,000	20,001 – 25,000	>25,000
WBC decrease - cells/mm ³	2,500 - 3,500	1,500 - 2,499	1,000 - 1,499	<1,000
Lymphocytes decrease - cells/mm ³	750 – 1,000	500 – 749	250 – 499	<250
Neutrophils decrease - cells/mm ³	1,500 - 2,000	1,000 – 1,499	500 – 999	<500
Eosinophils - cells/mm ³	650 - 1,500	1,501 – 5,000	>5,000	Hypereosinophilic
Platelets decreased - cells/mm ³	125,000 - 140,000	100,000 - 124,000	25,000 - 99,000	<25,000
Chemistry				
BUN - mg/dL	23 – 26	27 – 31	>31	Requires dialysis
Creatinine - mg/dL	1.5 – 1.7	1.8 – 2.0	2.1 – 2.5	>2.5 or requires dialysis
Alkaline phosphate – increase by factor	1.1 – 2.0 x ULN	2.1 – 3.0 x ULN	3.1 – 10 x ULN	>10 x ULN
Liver function tests – ALT, AST - increase by factor	1.1 – 2.5 x ULN	2.6 – 5.0 x ULN	5.1 – 10 x ULN	>10 x ULN
Bilirubin – when accompanied by any increase in liver function test - increase by factor	1.1 – 1.25 x ULN	1.26 – 1.5 x ULN	1.51 – 1.75 x ULN	>1.75 x ULN
Bilirubin – when liver function test is normal - increase by factor	1.1 – 1.5 x ULN	1.6 – 2.0 x ULN	2.0 – 3.0 x ULN	>3.0 x ULN

Table 7:	Laborator	v abnormalitv	grading	scale
		awnormancy	graamg	00010

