7.1. Appendix 1: Changes to protocol-planned analyses

Instead of AEs by grade, the overall AE table will include AEs with Grade \geq 3.

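### The SAP drops the protocol's worst-grade laboratory shift tables and grades only lymphocytes (1 of the 12 analytes in protocol Table 7), and Appendix 7.1 does not record the change.

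*SAP*

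**What the plan says.** Protocol section 9.4.5 (Other safety analyses) covers Group A and the Immunology Subgroup of Group B. It makes two commitments on laboratory severity. The first is grading: "Abnormal laboratory results will be graded using criteria based on the guidance given in FDA Guidance for Industry". The second is the display: "Shift tables from baseline to worst intensity grade will be provided for each laboratory parameter by group". Section 10.3.2.2 supplies the scale: "Laboratory abnormalities will be graded according to the grading scheme given in Table 7". Section 9.4.5 also leaves room for elaboration: "Clinical laboratory analysis details will be described in the SAP".

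SAP section 6.8.2 applies the scale to one analyte: "Abnormal lymphocytes data will be categorized as defined in table 7 in the protocol". The grades are used in one display, a frequency table by time point: "The same table will be provided for the grading scheme (grades mild, moderate, severe and life threatening) for lymphocytes". The shift analysis for each parameter is defined differently, as "shift tables from baseline to worst post-baseline value with respect to reference range values (low, normal, high), if applicable".

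The SAP introduction states that it is written for protocol version 4.0 and that changes from the protocol are documented in section 7.1. That appendix has one entry, about adverse events: "Instead of AEs by grade, the overall AE table will include AEs with Grade" 3 or higher. Laboratory grading is not mentioned.

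**The concern.** A reference-range category says on which side of normal a value lies, but not how far. For ALT, the Grade 1 band starts at 1.1 x ULN and Grade 4 is anything above 10 x ULN; the SAP shift table calls both high. The protocol's table would separate them and show how many subjects in each group moved to a worse grade.

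Safety is the primary objective and Group A is the only randomized comparison, so the number of subjects reaching Grade 3 or 4 on each vaccine is a natural thing to read from the laboratory output. Immune thrombocytopenia is an adverse event of special interest, yet platelets are among the ungraded analytes.

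The silence matters too. Protocol section 9.4 requires the clinical trial report to justify deviations from the analyses in the final SAP. An analysis dropped within the SAP, and not entered in Appendix 7.1, is not caught by that requirement.

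**Working it through.** No sample size, power or error-rate figure is involved. The check is a comparison of texts and a count.

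**Step 1. Plan against plan.**

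| Item | Protocol 9.4.5 and Table 7 | SAP 6.8.2 |
|---|---|---|
| Results graded | Abnormal results generally, on the Table 7 scale | Lymphocytes only |
| Shift table | Baseline to worst grade, each parameter, by group | Baseline to worst reference-range category |
| Worst-grade shift tables | One per parameter | None, including for lymphocytes |
| Change declared in SAP 7.1 | – | No |

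**Step 2. Analytes affected.** Table 7 has 10 hematology rows and 6 chemistry rows, 16 in all. Some analytes take several rows (hemoglobin by sex and by change from baseline, WBC up and down, bilirubin by liver test status), and one row serves both ALT and AST. The distinct analytes are:

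- Hematology: hemoglobin, WBC, lymphocytes, neutrophils, eosinophils, platelets = 6.
- Chemistry: BUN, creatinine, alkaline phosphatase, ALT, AST, bilirubin = 6.

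Total 6 + 6 = 12. The SAP grades 1, leaving 12 − 1 = 11.

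**Step 3. How much of the protocol's promise could be kept.** Protocol section 10.2 lists 10 hematology and 16 chemistry parameters (FSH aside), 10 + 16 = 26. Table 7 covers 12, so 26 − 12 = 14 have no grade in the protocol's own scale. These are hematocrit, red cell count, monocytes, basophils, ferritin, C-reactive protein, albumin, amylase, gamma glutamyl transpeptidase, glucose, lipase, sodium, potassium and calcium.

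**Step 4. What a shift table would show.**

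- ALT. Inclusion criterion 11 admits values below 3.0 x ULN. A subject entering at 2.9 x ULN is in Grade 2 (2.6–5.0 x ULN). A rise to more than 10 x ULN is Grade 4. The protocol's table shows Grade 2 to Grade 4; the SAP's shows high to high.
- Hemoglobin. Table 7 makes a fall of 2.1–5.0 g/dL from baseline Grade 3. If the later value is still within the laboratory's reference range (not given in the documents, so this is conditional), the SAP's table shows normal to normal.

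**Step 5. Where post-dose laboratory data exist.**

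- Group A (protocol Table 1): scheduled post-dose draws at Visits 4 and 7, and at early termination. At most 90 subjects, randomized 2:1, hence about 90 × 2/3 = 60 and 90 × 1/3 = 30.
- Group B transplant subjects (Table 2a): hematology at Visits 8, 9 and 10, up to 15 subjects.
- Other Group B subjects (Tables 2 and 3): scheduled laboratory tests at Visit 0 only, so scheduled data support no shift table of either kind.

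**The case against.** A reader might infer that severe laboratory changes will be tabulated only as high or low, or that they will appear in no summary comparing the two vaccines. The documents do not support that. For each parameter, SAP section 6.8.2 also counts clinically significant abnormal, not clinically significant abnormal, normal and missing values. It summarizes values and changes from baseline; under section 6.1.1 these summaries include minimum and maximum, and Group A is split by vaccine. Every value is listed with normal ranges and flags. An ALT above 10 x ULN at a scheduled visit would therefore be visible as a maximum. Clinically significant findings are also to be documented as adverse events and graded, and SAP section 6.4.3 tabulates treatment-emergent events by worst grade.

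These outputs remain, but they do not replace a count by grade. Clinical significance is an investigator's judgement in an open-label trial. A maximum shows one extreme value and not how many subjects reached a grade. The adverse event route omits abnormalities judged not clinically significant. Under protocol section 10.3.1.9, a laboratory abnormality that is a sign of a disease is recorded under the diagnosis alone. From Visit 5 onward in Group A, only related events, events of special interest, serious events and events linked to confirmed COVID-19 are recorded. An unrelated, non-serious laboratory abnormality found at Visit 7 would miss the adverse event tables.

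Two further points have force. The protocol's wording cannot be followed literally, since 14 of 26 parameters have no grade, and section 9.4.5 leaves details to the SAP. That justifies limiting graded tables to the Table 7 analytes. It does not explain stopping at lymphocytes, and protocol section 9.4 describes the SAP as a more detailed account of the planned analyses, which does not extend to removing one. The scope is also modest: laboratory values are other safety analyses, and the trial tests no hypothesis.

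**Conclusion.** The point holds as an undeclared difference between protocol and SAP that loses planned safety information. The SAP grades 1 of 12 gradable analytes, leaves 11 without any laboratory table by severity grade, and provides none of the worst-grade shift tables. Worsening within the high or low category shows as no shift.

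It should not be read as concealment of severe values or as a fault in the primary or secondary endpoints. Nor does it put a fixed width on what the high category hides: Grade 4 for ALT has no upper limit, so no ratio of grade limits measures the loss.

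The conclusion rests on the scheduled visits in protocol Tables 1 to 3 and on Table 7 as the only grading scale for laboratory values that the documents set out. The consequence is mainly for Group A by vaccine and for hematology in the transplant subjects. It should be corrected, at modest priority.

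**What to change.** In SAP section 6.8.2:

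- Apply Table 7 to all 12 analytes, and add a grade-frequency table by time point and a shift table from baseline to worst post-baseline grade. Do this wherever scheduled post-dose data exist: Group A by vaccine, and the 6 hematology analytes for Group B transplant subjects.
- Keep the reference-range shift tables for the 14 parameters without a Table 7 grade.
- State the derivation rules that Table 7 leaves open: how the absolute and change-from-baseline rows for hemoglobin combine, which bilirubin row applies, and how a bilirubin of exactly 2.0 x ULN with normal liver tests is assigned, since it falls in both the Grade 2 and Grade 3 bands.

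In SAP Appendix 7.1, record that worst-grade shifts are restricted to the Table 7 analytes, with the reason. If the sponsor prefers to grade lymphocytes only, that larger reduction should be declared and justified there.

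The cost is some programming and a few extra tables. The data are already collected and the thresholds are already in the protocol.
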